7.6 Secondary analyses

7.6.1 Efficacy

All secondary analyses will be exploratory and will be considered descriptively. Secondary parameters at baseline and during follow-up will be compared between groups comparing the difference between baseline and follow-up visits. Data will be displayed by means and standard deviations, or in case of non-normally distributed data with medians and variances. Changes will be displayed with means and standard deviations with respective 95% confidence intervals.

Secondary endpoints will be statistically analyzed by a hierarchical testing strategy using the two-sided student's t-test with comparison of the differences between riociguat (MK-4836) and placebo. p-values <0.05 will be considered as statistically significant.

The sequential testing procedure will be performed for these six secondary efficacy variables, strictly in the order listed

- change of cardiac index at rest (baseline to 24 weeks)
- change of total pulmonary resistance (baseline to 24 weeks)
- change of diffusion capacity of the lung (baseline to 24 weeks)
- change of 6-minute walking distance (baseline to 24 weeks)
- change of WHO functional class (baseline to 24 weeks)
- change in QoL (SF-36, physical summation score; baseline to 24 weeks)

Further outcome parameters will be tested exploratory and reported with 95% confidence intervals of the difference between changes in the intervention and placebo group, mean and standard deviation of the mean. Normally distributed data will be compared by two-sided student's t-tests or Welch-test in case of unequal variances. Non-normally distributed data will be analysed by nonparametric analysis methods such as the Wilcoxon-Mann-Whitney test. Frequency data will be compared by Chi square test, if preconditions are met. Parameters will

be analyzed as change from baseline to 24 weeks riociguat (MK-4836) vs. placebo; if available as per visit and assessment schedule, changes between baseline and 12 weeks will also be analyzed.

Patients who withdraw from the study will be asked to complete a final examination which will be included in the data analysis.

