If the true treatment effect is at least a 30% reduction of PVR (effect size is 0.87), a sample size of 29 patients/group (total 58 patients) achieves a statistical power of 90.2% to reject the null hypothesis, according to the two-sample student's t-test, with a type I error of 0.05 (two-sided). With the sample size of 70 patients and a dropout of 15% (valid sample size n=58), we achieve a 90.2% power, if the means of PVR differ by at least 30% and both groups have an equal standard deviation of 34.5%. A sample of 70 patients (35 patients in each group), allocated in a 1:1 ratio, will therefore be included.

The primary endpoint will be analyzed by an analysis of covariance (ANCOVA) with baseline values as covariates, which has a power advantage over the student's t-test, achieving a statistical power of 90.2% or more. If the preconditions for ANCOVA are not met, a student's t-test assuming unequal variances (Welch-test) will be performed.

EudraCT: 2021-001633-40	Version 1.7 15.01.2025	ESRA
-------------------------	---------------------------	------

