All secondary analyses will be exploratory and will be considered descriptively. Secondary parameters at baseline and during follow-up will be compared between groups comparing the difference between baseline and follow-up visits. Data will be displayed by means and standard deviations, medians and variances with respective 95% confidence intervals. p-values <0.05 will be considered as statistically significant.

Secondary endpoints will be statistically analyzed by a hierarchical testing strategy using the two-sided student's t-test with comparison of the differences between riociguat (MK-4836) and placebo.

The sequential testing procedure will be performed for these six secondary efficacy variables, strictly in the order listed

- change of cardiac index at rest (baseline to 24 weeks)
- change of total pulmonary resistance (baseline to 24 weeks)
- change of diffusion capacity of the lung (baseline to 24 weeks)
- change of 6-minute walking distance (baseline to 24 weeks)
- change of WHO functional class (baseline to 24 weeks)
- change in QoL (SF-36, physical summation score; baseline to 24 weeks)

It is assumed that WHO functional class will either remain the same, improve by one or two categories, or deteriorate by one category in most cases. A change score (baseline minus end of study) will be calculated, which could go from -3 (class IV at baseline and class I at end of study) to +4 (class I at baseline, death at end of study), but in practice for those patients still alive at the end of the study it will most likely range from -2 to +1.

EudraCT: 2021-001633-40	Version 1.7 15.01.2025	ESRA
-------------------------	---------------------------	------

Exploratory endpoints

Further outcome parameters will be tested exploratory and reported with 95% confidence intervals of the difference between changes in the intervention and placebo group, mean and standard deviation of the mean. Parameters will be analyzed as change from baseline to 24 weeks riociguat (MK-4836) vs. placebo; if available as per visit and assessment schedule, changes between baseline and 12 weeks will also be analyzed.

Patients who withdraw from the study will be asked to complete a final examination which will be included in the data analysis.

Parameters for explorative data analysis include

WHO functional class (baseline to 12 weeks)

Echocardiography

- sPAP, RV-area and RA-area, TAPSE, LV-EI, RV-pump function and LV-EF.

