5.3 Secondary analysis

5.3.1 Secondary efficacy endpoints

will be tested hierarchically:

- change of cardiac index at rest (baseline to 24 weeks)
- change of total pulmonary resistance (baseline to 24 weeks)
- change of diffusion capacity of the lung (baseline to 24 weeks)
- change of 6-minute walking distance (baseline to 24 weeks)

- change of WHO functional class (baseline to 24 weeks)
- change in QoL (SF-36, physical summation score; baseline to 24 weeks)

The following parameters will be assessed in every patient according to the visits schedule and analyzed as **exploratory variables**. Changes between groups will be compared by student's t-test or Welch-test if variances are not equal. Nonparametric data will be compared by Wilcoxon-Mann-Whitney test. Frequency data will be compared with chi-square tests. Exploratory endpoints will be analyzed as change from baseline to 12 and 24 weeks as available per assessment schedule. According to the study protocol, patients were encouraged to perform their final assessment visit in case of any premature termination of study treatment or study participation.

QoL assessed by the SF-36 questionnaire

Short form health survey 36, including 2 summation scores and 8 subscores.

QoL will be assessed using the SF 36-questionnaire that will be handed out to the patients. Scoring will be carried out according to the test manual.

The SF-36 consists of eight scaled scores, which are the weighted sums of the questions in their section. Each scale is directly transformed into a 0-100 scale, i.e. a score of zero is equivalent to maximum disability and a score of 100 is equivalent to no disability. The eight sections are: vitality; physical functioning; bodily pain; general health perceptions; physical role functioning; emotional role functioning; social role functioning; mental health.

WHO functional class

Analysis of changes between baseline and first/second follow-up.

Lung function and lung diffusing capacity

- FEV1 (forced expiratory volume in 1 second), TLC (total lung capacity), DLCO (diffusing capacity of the lung)

Echocardiography

- systolic pulmonary arterial pressure (sPAP, mmHg), right ventricular area (RV-area, cm²), and right atrial area (RA-area, cm²), tricuspid annular plane systolic excursion (TAPSE), left ventricular eccentricity index (LV-EI), RV-pump function and LV-pump function (LV-EF, %).

Analyses of blood samples

Venous blood will be analyzed to determine:

- NT-pro BNP

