7.8 Interim analyses

Not available

8 Deviations from the original protocol

The study was ended prematurely, leading to a sample size reduction to 35 patients (planned 70 patients).

The study was terminated early due to a strategic decision of MSD/Merck:

“After reviewing the timelines, remaining payments, and considering the changing landscape and altered feasibility of this study, a strategic prioritization was made to select this study for early termination.”

As a result of this decision, the final sample size reached 50% of the originally planned enrolment (n= 35). All statistical analyses will be conducted based on the available data at the time of study cessation. The reduction in sample size may limit the statistical power, particularly given the double blinded two-armed design of the study. According to the study protocol, patients were encouraged to perform their final assessment visit in case of any premature termination of study treatment or study participation. This data will be included into the final analysis according to the intention-to-treat principle.

Subgroup analyses may not be performed due to insufficient sample size.

9 Interpretation of results

Interpretation of data is limited by the early termination of the whole trial. This led to a reduction of sample size to 35 patients in total instead of per group, and to a premature study termination in a subset of patients. As the treatment effect is anticipated to be less distinct in a shorter period of time in the verum group and worsening of clinical parameters is expected to be less pronounced in the control group, early study termination will reduce the effect size and does therefore not bear the risk of overestimation of the clinical effects of the study treatment. A shorter study duration is expected to reduce the statistical power (reduction of sample size and effect size).

Safety data will comprise of less investigational medicinal production exposition than planned. As the study medication is already an approved treatment and extensive data on safety and tolerability is already available, a substantial impact on safety and tolerability results of the study is not anticipated.

Due to the reduced sample size, subgroup analyses such as centre effects may not be further analysed as sample sizes for each center and for hemodynamics subgroups are not high enough.

10 Data problems

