Analysis of PVR distribution identified an outlier at visit 3, which could be corrected by calculation of PVR from the formula $PVR = (mPAP - PAWP) / CO * 80$

PVR was therefore recalculated for all values at visit 3.

11 Software

Data analysis with SPSS V29, IBM Somers, New York.

12 References

NA

13 Appendices – List of Tables

All tables with mean \pm standard deviation or n and % for frequency data.

Tables with comparisons between groups will additionally include p-values and 95% confidence intervals.

Table 1. Demographics and Baseline Characteristics for the whole dataset and by group.

(table may be split for better readability)

Female sex no. [%]

Age [years]

Height [cm]

Weight [kg]

PH duration [months]

Vital

signs

Systolic blood pressure

Diastolic blood pressure

SpO₂ [%]

Heart rate

WHO FC no. [%]

I

II

III

IV

PAH Etiology

Idiopathic

Heritable

CTD-associated-PAH

Other

Concomitant diseases

Blood gas analysis

SaO₂ [%]

PaO₂ [mmHg]

PaCO₂ [mmHg]

pH

Bicarbonates

Hemodynamics at rest

RAP [mmHg]

sPAP [mmHg]

dPAP [mmHg]

mPAP [mmHg]

PAWP [mmHg]

CO [l/min]

CI [l/min/m²]

PVR [WU]

SvO₂ [%]**6MWD**

6MWD [m]

SpO₂ [%] test end

Borg dyspnea score

Short Form-36 Health Survey

Physical functioning

Physical role function

Pain

General health perception

Vitality

Social functioning

Emotional role function

Mental well-being

Physical summation score

Mental summation score

Echocardiography at rest

Estimated sPAP [mmHg]

RA area [cm²]RV area [cm²]

TAPSE [cm]

LV-EI

Left ventricular ejection fraction [%]

Lung function

FVC [L]

FEV1 [%predicted]

TLC [%predicted]

Residual Volume [%predicted]

DLCO % predicted

DLCO VA % predicted

Laboratory

Hemoglobin [g/dl]

Creatinine [mg/dl]

Urea [mg/dl]

Uric acid [mg/dl]

SGPT [U/l]

CRP [mg/l]

NTproBNP [pg/ml]

Table 2**Comparison of changes between groups****WHO FC Change (Visit 1-2)**

Improvement (- 1)

Worsening (+1)

Unchanged

Blood gas analysis

SaO2 [%]

PaO2 [mmHg]

PaCO2 [mmHg]

pH

Bicarbonates

Hemodynamics at rest

RAP [mmHg]

sPAP [mmHg]

dPAP [mmHg]

mPAP [mmHg]

PAWP [mmHg]

CO [l/min]

CI [l/min/m²]

TPR mmHg [min l- 1]

PVR [WU]

SvO2 [%]

6MWD

6MWD [m]

Short Form-36 Health Survey

Physical functioning

Physical role function

Pain

General health perception

Vitality

Social functioning

Emotional role function

Mental well-being

Physical summation score

Mental summation score

Echocardiography at rest

Estimated sPAP [mmHg]

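### The ranked secondary endpoints are compared by an unadjusted t-test on change although the primary uses ANCOVA; the WHO functional class change label is reversed, and Table 2 omits its 24-week result

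*SAP*

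**What the plan says.** **Test for the ranked secondaries.** SAP 7.6.1 and Protocol 10.3.1 both specify a hierarchical strategy "using the two-sided student's t-test with comparison of the differences between riociguat (MK-4836) and placebo". No covariate is mentioned. The fixed order is cardiac index, total pulmonary resistance, diffusion capacity, 6-minute walking distance, WHO functional class and SF-36 physical summation score, each at 24 weeks and each judged at p<0.05. The same SAP section says: "All secondary analyses will be exploratory and will be considered descriptively".

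**Test for the primary.** SAP 7.5 and Protocol 10.3.1 use ANCOVA with baseline as covariate and fall back to the Welch test if its preconditions fail. Protocol 10.1 and SAP 5.1.1 say of this ANCOVA that it is a method "which has a power advantage over the student's t-test".

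**WHO functional class score.** Protocol 10.3.1 states: "A change score (baseline minus end of study) will be calculated, which could go from -3 (class IV at baseline and class I" at the end. It gives the other extreme as +4, for class I at baseline followed by death. For survivors it expects that "it will most likely range from -2 to +1". The SAP has no formula for this score and no value for death.

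**Table shell.** SAP section 13, Table 2, has one WHO class block, headed "WHO FC Change (Visit 1-2"), with rows for improvement (-1), worsening (+1) and unchanged.

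**Rank test.** For exploratory variables SAP 5.3.1 says: "Nonparametric data will be compared by Wilcoxon-Mann-Whitney test".

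**The concern.** Baseline is measured for every ranked endpoint, so leaving it out of the model discards information already collected. SAP section 3 puts enrolment at 35 of a planned 70, and section 9 reports "premature study termination in a subset of patients". In a sample this small a chance baseline difference between arms can be sizeable, and a change score corrects for it only in part or overcorrects. Because testing runs in strict order from cardiac index, avoidable imprecision there can end the sequence before the other five endpoints are reached.

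The WHO class points are different in kind. A score programmed from the protocol's label would have the opposite sign to the protocol's own examples and to SAP Table 2, so an improvement could be reported as a worsening. And the table shell, as drafted, would not display the ranked WHO class result.

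**Working it through.** **Inputs from the documents.** Two-sided alpha 0.05. Planning values for the primary: difference 30%, SD 34.5%, 29 evaluable per arm, stated power 90.2% (SAP 5.1.1). Enrolled: 35 (SAP section 3).

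**Assumptions, because the documents are silent.** Arms of 17 and 18; baseline-to-follow-up correlation rho from 0.3 to 0.9; ratio of follow-up to baseline SD, k, of 1 or 1.25.

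**The plan's own figure.** With d = 30/34.5 = 0.87, 29 per arm and 56 df, the noncentral t distribution gives 90.2%, as stated. No power is stated for any secondary endpoint.

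**Precision of ANCOVA against the t-test on change.**

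1. Large-sample variance ratio: Var(ANCOVA)/Var(change) = k²(1 − rho²)/(1 + k² − 2k·rho). For k = 1 this is (1 + rho)/2.
2. Cost of estimating the slope: multiply by 1 + 1/(N − 4), which is 1.032 at N = 35 and 1.038 at N = 30.
3. Interval width: take the square root and multiply by the ratio of t quantiles for N − 3 and N − 2 df (2.037/2.035 = 1.001 at N = 35).

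For k = 1, rho = 0.5, N = 35: 0.75 × 1.032 = 0.774; √0.774 × 1.001 = 0.881, so 11.9% narrower.

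| N = 35 | rho 0.3 | rho 0.5 | rho 0.8 | rho 0.9 |
|---|---|---|---|---|
| k = 1, large-sample ratio | 0.650 | 0.750 | 0.900 | 0.950 |
| k = 1, with slope cost | 0.671 | 0.774 | 0.929 | 0.981 |
| k = 1, change in CI width | −18.0% | −11.9% | −3.5% | −0.9% |
| k = 1.25, large-sample ratio | 0.784 | 0.893 | 1.000 | 0.950 |
| k = 1.25, with slope cost | 0.810 | 0.922 | 1.032 | 0.981 |
| k = 1.25, change in CI width | −9.9% | −3.9% | +1.7% | −0.9% |

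At N = 30 the extremes are −17.7% (k = 1, rho 0.3) and +2.1% (k = 1.25, rho 0.8). Simulation at N = 35 (6,000 runs) gave variance ratios of 0.66 (k = 1, rho 0.3), 0.78 (k = 1, rho 0.5) and 1.03 (k = 1.25, rho 0.8), in line with the table.

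**Power, as illustration only.** Borrowing d = 0.87 from the primary, with 17/18 and k = 1, the t-test has 70.4% power. ANCOVA, with the slope cost included, has about 86%, 81%, 76% and 71% at rho 0.3, 0.5, 0.7 and 0.9; simulation gave 86.3%, 81.3%, 76.1% and 71.7%.

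**Chance imbalance.** One standard error of the baseline difference is √(1/17 + 1/18) = 0.34 SD. With k = 1, such a difference moves the change-score estimate by √((1 − rho)/2) of its own standard error: 0.59, 0.50 and 0.22 at rho 0.3, 0.5 and 0.9.

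**Direction of the WHO class score, scoring death as 5.**

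| Course | Baseline minus end (the label) | End minus baseline | Printed |
|---|---|---|---|
| Class IV to class I | 4 − 1 = +3 | 1 − 4 = −3 | −3 |
| Class I to death | 1 − 5 = −4 | 5 − 1 = +4 | +4 |

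Both printed extremes match end minus baseline. So do Table 2, where improvement is −1, and the expected range of −2 to +1, which sits beside a statement that patients may improve by one or two classes or worsen by one.

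**Table 2.** The ranked endpoint is baseline to 24 weeks, which is Visit 3. Visit 2 is week 12, listed in Protocol 10.3.1 as exploratory. The Visit 1-2 heading cannot be shorthand for all follow-up, because the laboratory block in the same table is marked V1-3. The other five ranked endpoints have rows. The WHO class block has no row for a two-class improvement, which the protocol expects, or for death, which it scores.

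**The case against.** The strongest reply is that the documents do not contradict each other on the test. Protocol and SAP name the same t-test, and the remark about ANCOVA's power concerns the primary endpoint only. A t-test on change is unbiased under randomisation. The secondaries are called exploratory and intervals will be reported whatever the sequence does, so the practical loss is limited. The gain depends on correlations that nobody has stated and is close to nil if they are high. Precision and protection from imbalance are also one benefit seen twice: at k = 1 the squared imbalance shift, (1 − rho)/2, equals the large-sample variance reduction. All of this stands. It makes the point an avoidable inefficiency and not an error, and the two gains should not be added together.

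Replacing a protocol test late also has a cost. Enrolment has ended, and SAP section 10 shows that Visit 3 PVR values have been inspected. SAP 1.3 says the statistician will be blinded during the analysis, but that is a plan, so the change must depend on blinding still being intact. Moving to ANCOVA should also bring a fallback like the primary's.

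On WHO class, the worked cases in the protocol and the signs in Table 2 make the intended direction clear, and a two-sided p-value does not depend on sign. SAP 5.3.1 plans the analysis at both follow-ups, so the Visit 1-2 block is legitimate in itself. The label is nevertheless wrong, and the 24-week block is still missing. The rank test is closer to a preference: no gain in power or error rate has been shown for it on a heavily tied score.

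**Conclusion.** The point holds and should be acted on. For the five continuous ranked endpoints, adjustment for baseline offers a moderate gain if the correlation is low (CI up to 18% narrower at rho 0.3 and k = 1) and almost none if it is high. The worst loss in the scenarios examined is about 2% of CI width. These sizes rest on assumed rho, k and arm sizes; the direction of the trade, a possible useful gain against a very small cost, does not depend on fine detail within that range.

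The reversed label in Protocol 10.3.1 and the missing 24-week WHO class block in SAP Table 2 are plain errors of drafting that need no assumption beyond death being scored as 5, which the printed +4 implies. They do not alter a two-sided p-value, but they affect what is reported and in which direction.

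**What to change.** 1. **SAP 7.6.1.** Analyse cardiac index, total pulmonary resistance, diffusion capacity, 6-minute walking distance and SF-36 physical summation score by ANCOVA of the 24-week change, with treatment and that endpoint's own baseline. Keep the order and alpha, and keep the t-test as a sensitivity analysis. The primary's Welch fallback can be carried over.
2. **SAP section 8.** Record this as a departure from the protocol's t-test, decided before unblinding. If unblinding has already happened, leave the t-test in place and report ANCOVA as supplementary only.
3. **WHO functional class.** Define the change in the SAP as end of study minus baseline, with death scored as 5, and correct the label in Protocol 10.3.1. Use the Wilcoxon-Mann-Whitney test for the ranked comparison.
4. **SAP Table 2.** Add a Visit 1-3 WHO class block with a row for every possible change, including −2 and death.

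The cost is wording in SAP 7.6.1, section 8 and Table 2, one corrected label in the protocol, one degree of freedom per model and a disclosed departure from the protocol's test. No further data collection is needed.

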8.4.1 Efficacy Parameters

The primary efficacy variable is the change in pulmonary vascular resistance from baseline to week 24.

Secondary efficacy endpoints will be tested hierarchically:

EudraCT: 2021-001633-40	Version 1.7 15.01.2025	ESRA
-------------------------	---------------------------	------

- change of cardiac index at rest (baseline to 24 weeks)
- change of total pulmonary resistance (baseline to 24 weeks)
- change of diffusion capacity of the lung (baseline to 24 weeks)
- change of 6-minute walking distance (baseline to 24 weeks)
- change of WHO functional class (baseline to 24 weeks)
- change in QoL (SF-36, physical summation score; baseline to 24 weeks)

Exploratory endpoints

The following parameters will be assessed in every patient according to the visits schedule and analyzed as **exploratory variables**. Exploratory endpoints will be analyzed as change from baseline to 12 and to 24 weeks as available according to assessment schedule.

QoL assessed by the SF-36 questionnaire

- mental summation score as well as the 8 sub scores

WHO functional class

Echocardiography

- systolic pulmonary arterial pressure (sPAP, mmHg), right ventricular area (RV-area, cm²), and right atrial area (RA-area, cm²), tricuspid annular plane systolic excursion (TAPSE), left ventricular eccentricity index (LV-EI), RV-pump function and LV-pump function (LV-EF, %).

Lung function

- FEV1 (forced expiratory volume in 1 second), TLC (total lung capacity), DLCO (diffusing capacity of the lung)

Analyses of blood samples

Venous blood will be analyzed to determine:

- NT-pro BNP

Blood for blood gas analyses

- oxygen partial pressure, carbon dioxide partial pressure, oxygen saturation of the blood (SpO₂), pH values, bicarbonates, base excess

Pulmonary hemodynamics by right heart catheterization

- sPAP, mPAP, diastolic pulmonary artery pressure (dPAP), pulmonary artery wedge pressure (PAWP), right atrial pressure (RAP), cardiac output and ejection fraction (CO), central venous saturation, via blood gas analysis from pulmonary artery (SvO₂)

EudraCT: 2021-001633-40	Version 1.7 15.01.2025	ESRA
-------------------------	---------------------------	------

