With the sample size of 70 patients and a dropout of 15% (valid sample size n = 58), a 90.2% power will be achieved to reject the null hypothesis, if the true treatment effect is at least a 30% reduction of PVR and both groups have an equal standard deviation of 34.5%, according to the two-sample student's t-test, with a type I error of 0.05 (two-sided). A sample of 70 patients (35 patients in each group), allocated in a 1:1 ratio, was therefore aimed to be included.

The primary endpoint will be analyzed by an analysis of covariance (ANCOVA) with baseline values as covariates, which has a power advantage over the student's t-test, achieving a statistical power of 90.2% or more. If the preconditions for ANCOVA are not met, a student's t-test assuming unequal variances (Welch-test) will be performed.

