7.5 Primary analysis

Null-Hypothesis (H_0):

The means of the treatment and control group of the primary endpoint is the same at baseline and after 24 weeks.

Alternative hypothesis (H_1):

The mean of the treatment group of the primary endpoint after 24 weeks differs from the mean of the control group.

Type I error

If not mentioned otherwise, all statistical tests will be performed with a type I two-sided error rate of $\alpha = 0.05$

The evaluation of the primary efficacy endpoint will be the change from baseline to 24 weeks in pulmonary vascular resistance. The primary analysis set will be a complete case analysis of the intention-to-treat set.

The main comparison will be the difference in treatment effect between riociguat (MK-4836) and placebo. 95% confidence intervals of treatment difference will also be calculated. The primary comparison will be an ANCOVA model including baseline scores as covariate.

If the preconditions for an ANCOVA analysis are not met, the primary endpoint will be analyzed by robust, two-sided t-test (Welch-test).

A multiple imputation strategy will be implied and analyzed for the primary endpoint (25 imputations) in case of missing data for the primary endpoint.

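### The six secondary endpoints are labelled exploratory yet tested in a fixed sequence with p<0.05 called significant, and the sequence is not made conditional on the primary PVR result

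*SAP*

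**What the plan says.** SAP 7.6.1 makes three statements about the same six endpoints (cardiac index, total pulmonary resistance, diffusion capacity, 6-minute walking distance, WHO functional class, SF-36 physical summation score):

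- Status: "All secondary analyses will be exploratory and will be considered descriptively".
- Procedure: "The sequential testing procedure will be performed for these six secondary efficacy variables, strictly in the order listed".
- Decision rule: "p-values <0.05 will be considered as statistically significant".

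Protocol 10.3.1 carries the same exploratory label, order and threshold: "Secondary endpoints will be statistically analyzed by a hierarchical testing strategy using the two-sided student's t-test". Protocol 8.4.1 says only "Secondary efficacy endpoints will be tested hierarchically"; the protocol synopsis, protocol 3.2 and SAP 5.3.1 add no rule beyond that.

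The primary analysis is a single test: "The primary comparison will be an ANCOVA model including baseline scores as covariate" (SAP 7.5). The error rate is given per test: "If not mentioned otherwise, all statistical tests will be performed with a type I two-sided error rate of" 0.05.

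Three things are written in neither document: a condition that the primary must succeed before the sequence starts, an explicit stop at the first non-significant endpoint, and the family of hypotheses that the ordering protects.

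**The concern.** A strict order and a significance threshold do no work if the six endpoints are only described. SAP 7.6.1 also sets these six apart from further outcome parameters, which it says are tested in an exploratory way, so the six appear to rank higher. The text therefore supports two reports of the same data. One analyst would give estimates and call nothing significant. Another would run the sequence and call cardiac index significant at p<0.05.

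The case that matters is a non-significant PVR result followed by p<0.05 for cardiac index. Nothing written prevents that from being presented as a positive result of a pre-specified hierarchy, and the SAP does not say how it should be reported. The primary test's own 5% level is not affected.

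**Working it through.** **Inputs from the documents.** Two-sided 0.05 per test (SAP 7.5); one primary test; six ordered secondaries (SAP 7.6.1); difference 30%, SD 34.5% in both groups, 58 evaluable patients (SAP 5.1.1), which is 29 per group (protocol 10.1); planned dropout 15%; cited WU-scale effect size 0.77 and planning effect size 0.87 (SAP 5.1.1); 35 patients enrolled (SAP sections 3 and 8). **Assumed:** the correlations between test statistics, and the numbers analysed at the achieved size.

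**1. The plan's own figure.** SAP 5.1.1 says "a 90.2% power will be achieved to reject the null hypothesis, if the true treatment effect is at least a 30% reduction of PVR". With d = 30/34.5 = 0.870 and 29 per group, the noncentrality is 0.870 × √(29×29/58) = 3.31 on 56 degrees of freedom. The noncentral t distribution gives 90.2%, so the figure reproduces.

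**2. Error within the six secondaries, stopping implied.** A false rejection requires the first true null hypothesis in the order to be rejected, which has probability at most 0.05. Family-wise error over the six is therefore 5%, with or without a condition on the primary.

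**3. Error over primary plus secondaries, no condition on the primary.** Suppose no endpoint is affected. With stopping, at least one false claim occurs exactly when the primary or the first secondary reaches p<0.05:

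P = 0.05 + 0.05 − P(both significant)

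| Assumed correlation | P(both) | P(at least one) | P(primary fails, cardiac index significant) = 0.05 − P(both) |
|---|---|---|---|
| 0 | 0.0025 | 0.0975 | 0.0475 |
| 0.5 | 0.0093 | 0.0907 | 0.0407 |
| 0.7 | 0.0165 | 0.0835 (0.08345 before rounding) | 0.0335 (0.03345 before rounding) |

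P(both) is the bivariate normal probability that both statistics exceed 1.96 in absolute value. At independence, P(at least one) = 1 − 0.95² = 0.0975. The upper bound is 0.05 + 0.05 = 0.10.

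**4. With the condition on the primary and a stop rule.** The primary becomes step 1, so error over all seven tests is 5% at any correlation.

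**5. How likely a failed primary is.** Two-sample t-test, two-sided 0.05, noncentrality d × √(n₁n₂/(n₁+n₂)):

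| Analysed | d = 0.77 | d = 0.87 |
|---|---|---|
| 17 and 18 (all 35) | 2.28 → 59.9% | 2.57 → 70.4% |
| 15 and 15 (35 × 0.85 = 29.75, taken as 30) | 2.11 → 53.0% | 2.38 → 63.3% |

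The chance of failure when the effect is real is therefore about 40-47% at 0.77 and 30-37% at 0.87. ANCOVA may lower it; the documents give no baseline correlation from which to say by how much.

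**The case against.** The strongest reply is that the procedure works for the family it names. SAP 7.6.1 defines the sequence for the six secondaries. Words such as hierarchical, sequential and strictly in order imply stopping at the first failure, and step 2 shows that such a sequence holds 5% within the six. **This stands.** A reader might infer that the sequence fails to control the error it exists to control; the documents do not support that. Nor do they support reading the unstated stop rule as no stopping at all, which would give 1 − 0.95⁶ = 26.5% for six independent tests.

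Second, no family-wise 5% is promised. The 0.05 is per test, so 9.75% is not a breach of a stated rate. **This stands too.** The figure shows what the missing condition costs if study-wide control is wanted.

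Third, most of the 9.75% is the primary's own 5%. The specific false-positive path, a failed primary followed by a significant cardiac index, has probability 3.3-4.75% when nothing works. The 30-47% failure rates apply when the drug does work, and a significant cardiac index need not then be false. **Correct:** the two sets of figures answer different questions and should not be combined.

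Fourth, in a phase IIa trial ordered p-values can be read as exploratory throughout, and SAP section 9 already limits interpretation because of early termination. This weakens the concern but does not remove it. The text still attaches the term statistically significant to p<0.05 for these endpoints and says nothing about the primary.

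**Conclusion.** The concern holds as a conflict of rules with a missing condition. The exploratory label and the significance rule cannot both govern the six endpoints, and as written a secondary can be called significant after a failed primary.

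With stopping implied, error is 5% within the six. Over primary plus secondaries, with no effect on any endpoint, it is 9.75% if the tests are independent, about 9.1% and 8.3% at correlations of 0.5 and 0.7, and at most 10%. The correlations are assumptions. The situation is realistic at the achieved size: t-test power for the primary is about 53-60% at effect size 0.77 and 63-70% at 0.87, for 15 per group up to 17 and 18 analysed, before any ANCOVA gain.

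A reader might also infer that the secondaries are promised as purely descriptive. The text says exploratory and considered descriptively, which leaves the standing of p<0.05 unclear and does not rule it out.

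**What to change.** In SAP 7.6.1, with matching wording in protocol 10.3.1, state that:

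- the sequence starts only if the primary PVR analysis has p<0.05;
- it stops at the first endpoint with p>=0.05;
- all later p-values are nominal;
- the term statistically significant is used only for endpoints reached in this way.

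The exploratory label may stay. Removing it is not needed, and would be debatable in a trial cut to 35 patients. The change should be made before the blind is broken.

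The cost is a few sentences in each document and no new data. The downside is that if the primary fails, no secondary endpoint can be called significant; estimates with 95% confidence intervals would still be reported for all six.
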